2.2.7.1 Quality of Life

The QoL score at each time point will be summarized in terms of mean and standard deviation by treatment arm and treatment by stratified health status.

Early effects (QoL at 6 months), late effects (QoL at 24 months), and longitudinal effects (effect over 24 months) for the Minnesota Living with Heart Failure QoL data will also be assessed by a longitudinal repeated measures mixed effects analysis.

The outcome variable in the mixed models will be the change in the MLHF QoL score at each follow-up visit relative to baseline, which is a continuous variable. Model building methods will be used to first determine the most parsimonious covariance structure for the data. The model will first be fit with an unstructured covariance matrix with time treated as a categorical variable. The mixed model will include the following covariate: baseline MLHF score (continuous variable), site as a random effect, and general health status (Charlson co-morbidity index) as a fixed effect and time, along with a time and treatment interaction term. A second model will be fit with an unstructured covariance matrix with time treated as a linear trend. The model will include treatment, time, and the treatment by linear time interaction plus the pre-determined covariates. A likelihood ratio test (LRT) will then be performed to determine if the linear trend (plus its interaction with treatment) is consistent with the data. If the simpler model with time as linear is sufficient, time will be treated continuously. If the fit is significantly improved with time as a categorical effect, then time will be included in the model as a categorical variable.

Once the mean structure of the model is determined, a LRT will be performed to determine whether a more parsimonious covariance structure e.g. autoregressive covariance structure 1 (AR1) or AR1 or compound symmetry (CS), will fit better. Once the mean and covariance structure are identified for this model, a treatment by time interaction will be examined. If the interaction term is not significant, it will be removed

from the model. If the treatment by time interaction is significant, then pairwise treatment comparisons will be performed at each time point separately.

As discussed previously, the Charlson score is originally a continuous variable. We will also perform the mixed model analysis without dichotomizing general health status. In addition, graphical methods will be used to summarize the estimates of least square means and standard deviation, with pairwise comparisons at each time point.

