Early effects (QoL at 6 months), late effects (QoL at 24 months), and longitudinal effects (effect over 24 months) for the Minnesota Living with Heart Failure QoL data will also be assessed by a longitudinal repeated measures mixed effects analysis. All mixed models will be adjusted for the baseline Minnesota Living with Heart Failure score, and for the randomization design (site and co-morbidity burden). Site will be included in the model as a random effect and general health status (Charlson <3 versus ≥ 3) as a fixed effect. The outcome variable in the model will be the change in the Minnesota Living with Heart Failure Quality of Life Score at each follow-up contact relative to baseline. Model building methods will be used to first determine the best mean structure of the outcome (e.g., time as linear or categorical) and then to determine the best fitting and most parsimonious covariance structure for the data.

b) All-cause Hospitalization

Total hospitalizations, total number of days of hospitalization, and the proportion of participants who require at least one hospitalization during the follow-up period will be compared between treatment groups at a 0.05 significance level. No adjustment will be made for multiple testing for tertiary outcomes because they are considered exploratory in nature. The total hospitalizations and total days of hospitalization will be analyzed using generalized Poisson or negative binomial regression models. Proportion of participants requiring at least one hospitalization will be analyzed using a chi-square test statistic.

c) Sudden Cardiac Death

Time to event for sudden cardiac death will be analyzed using the same methodology described for the primary outcome at a 0.05 2-sided significance level. VA Vital Status File will be used to determine the vital status of all study participants who are lost to follow-up at study exit. VA Vital Status File search plus a NDI Plus database search for all participants who are found to have died through the VA database search in order to adjudicate the cause of death.

5. Analysis of Safety Data

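### The exploratory quality-of-life mixed model sets out to estimate separate 6- and 24-month effects, but forces them to be equal whenever the treatment-by-time term is not significant

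*Combined protocol and SAP*

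**What the plan says.** SAP 2.2.7.1 gives the purpose of the longitudinal model as "Early effects (QoL at 6 months), late effects (QoL at 24 months), and longitudinal effects (effect over 24 months"). It then sets out a sequence of choices made on the trial data:

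- **Time.** Linear is compared with categorical time by likelihood ratio test: "If the simpler model with time as linear is sufficient, time will be treated continuously".
- **Covariance.** "Once the mean structure of the model is determined, a LRT will be performed to determine whether a more parsimonious covariance structure" (AR1 or compound symmetry) fits better than unstructured.
- **Treatment by time.** "If the interaction term is not significant, it will be removed" from the model. Otherwise, "If the treatment by time interaction is significant, then pairwise treatment comparisons will be performed at each time point separately".

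The last paragraph of the same section adds, with no condition, that "graphical methods will be used to summarize the estimates of least square means and standard deviation, with pairwise comparisons at each time point". It does not say which model these come from.

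Protocol XV.C.4.a lists the same three targets and also chooses structure from the data ("Model building methods will be used to first determine the best mean structure of the outcome"). It has no rule for dropping the interaction; that rule appears only in the SAP.

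**The concern.** Without the treatment-by-time term, the model has a single treatment coefficient. The estimated difference is then identical at 6, 12 and 24 months, so two of the three stated targets are no longer estimated separately. A non-significant interaction does not show that the effects are equal; it may only mean that the test lacked power.

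The unconditional visit comparisons at the end of the section do not settle this. Taken from the model without the interaction, they repeat one number three times. Taken from any other model, they conflict with the conditional rule just above them.

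What is at stake is the reading of an effect that comes early and fades, or emerges late. It could be reported as a smaller effect at both visits, with an interval that takes no account of the preliminary test.

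**Working it through.** **Inputs from the documents.** SD of MLHF change 5 and a detectable difference of 0.73 with 80% power at 12 months (protocol XV.A.3); 731 per arm (protocol III.E); visits at 6, 12 and 24 months (protocol XI.A and XI.B.1).

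**Assumptions, because the documents give no figure.** True effects of 0.73, 0.365 and 0 at the three visits; equal correlation r between visits, 0.3 to 0.7; interaction test at 0.05; no missing data.

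**1. The plan's own figure.** The standard error of a difference at one visit is 5 × √(2/731) = 0.2615. The detectable difference is (1.960 + 0.842) × 0.2615 = 0.733, and power for 0.73 is 79.7%. The plan's figure is reproduced. It belongs to the 12-month secondary test and is used here only for scale.

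**2. What the reduced model estimates.** Under equal correlation, the common coefficient is the plain average of the visit effects: (0.73 + 0.365 + 0)/3 = 0.365. The truth is 0.73 at 6 months and 0 at 24 months.

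**3. How often the term is dropped.** Let v = 2 × 25/731 = 0.0684.

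- Categorical time, 2 df: noncentrality = Σ(effect − mean)² / [v(1 − r)] = 0.26645 / [0.0684(1 − r)].
- Linear time, 1 df: months centred at their mean of 14 are −8, −2 and 10, with sum of squares 168. The cross-product with the effects is −8(0.73) − 2(0.365) = −6.57. So z² = (6.57²/168) / [v(1 − r)] = 0.2569 / [0.0684(1 − r)].

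| r | 2-df noncentrality | significant | missed | 1-df z | significant | missed |
|---|---|---|---|---|---|---|
| 0.3 | 5.57 | 55.0% | 45.0% | 2.32 | 63.9% | 36.1% |
| 0.5 | 7.79 | 70.5% | 29.5% | 2.74 | 78.3% | 21.7% |
| 0.7 | 12.99 | 90.8% | 9.2% | 3.54 | 94.3% | 5.7% |

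The 1-df column matters because the SAP settles the form of time before it tests the interaction, and this effect pattern is nearly linear in months.

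**4. Behaviour of the whole rule, 2-df version.** In 400,000 simulated trials per setting, visit estimates were used when the interaction was significant and the common estimate otherwise.

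| r | 95% interval coverage at 6 months | false rejection at 24 months |
|---|---|---|
| 0.3 | 75.6% | 24.3% |
| 0.5 | 85.0% | 15.0% |
| 0.7 | 92.6% | 7.4% |

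If the term is always kept, coverage is 95% and false rejection 5%. The 1-df version of the whole rule was not simulated.

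**5. The opposite case.** If the effect is 0.73 at every visit, the rule is unbiased, and power at a given visit is 92% against 80% with the term kept (r = 0.5). With no effect at any visit, rejection is 5.4-5.9% over the same range of r.

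**The case against.** The case for leaving the plan alone has real content.

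- **The section is exploratory.** The secondary QoL comparison in SAP 2.2.6.2 is a separate 12-month t-test or rank-sum test, which the rule does not touch. This stands, and it limits the weight of the point.
- **Visit-level data are reported anyway.** SAP 2.2.7.1 and Table 26 give means and SDs at each visit by arm. That stands too, but these are unadjusted summaries, not model contrasts with intervals.
- **Dropping the term can help.** Under a constant effect it gains power without bias, as step 5 shows. A reader might infer that the simpler model has nothing to offer; that is wrong. The gain can be kept without a preliminary test by also reporting the average over visits.
- **The over-time target survives.** The common coefficient is close to an effect over 24 months. A reader might infer that the analysis cannot answer its own question at all. The documents do not support that: one of three targets is still met, and at SD 5 the term is retained in most trials under the illustration.

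A reader might also infer that the choice of linear time or covariance removes the visit effects. It does not. Linear time with its interaction still gives 6- and 24-month effects, constrained to a straight line, and covariance choice mainly affects standard errors. These are lesser points, as are some loose ends: the interaction test level is not stated, and AR1 and compound symmetry are not nested, so a likelihood ratio test cannot choose between them.

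Finally, a reader might take a larger SD and conclude that a real early effect is nearly always lost. At an assumed SD of 10, the 2-df test is significant in only 17-35% of trials. But the model that keeps the term then has just 29% power for 0.73 at 6 months, so much of that loss comes from a small effect rather than from the rule. The only SD in the documents is 5.

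**Conclusion.** The point holds in a limited form. SAP 2.2.7.1 names separate early and late effects as targets, and its drop rule makes them equal whenever the interaction is not significant. Its closing promise of visit comparisons either repeats one difference or conflicts with the rule.

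Under the illustrated fading effect at the plan's SD, the term is missed in roughly 9-45% of trials (2 df) or 6-36% (1 df). With the 2-df rule, coverage at 6 months is 76-93% and false rejection at 24 months is 24-7%. These sizes rest on the assumed effect pattern, the correlation range and complete data. Deaths and missed visits would lower the power of the interaction test and so make dropping more frequent.

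No primary or secondary conclusion changes. This is a worthwhile improvement to an exploratory analysis, not a threat to the trial.

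**What to change.** In SAP 2.2.7.1:

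- Delete the rule that removes a non-significant interaction, and the condition that visit comparisons need a significant one.
- Fix one model in advance: change in MLHF on treatment, categorical visit, treatment by visit (always kept), baseline MLHF, Charlson stratum and site as a random effect. Use unstructured within-patient covariance, and name a fallback if it does not converge.
- Report the 6-, 12- and 24-month contrasts and their average over visits, each with a 95% confidence interval, whatever the interaction p-value.
- State that the least square means and visit comparisons in the closing paragraph come from this model.

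The cost is SAP wording and somewhat less programming; no new data are needed. An unstructured matrix for three visits has six parameters.

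The downside is small. When the effect is constant, a visit contrast is less precise than a common effect: standard error 0.2615 against √[v(1 + 2r)/3], which is 0.191 at r = 0.3 and 0.234 at r = 0.7. That makes visit intervals about 37% to 12% wider. Reporting the average alongside offsets this.

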2.2.7.2 All-cause Hospitalization

Total hospitalizations, total number of days of hospitalization, and the proportion of participants who require at least one hospitalization during the follow-up period will be summarized by treatment and compared between treatment groups at a 0.05 significance level. No adjustment will be made for multiple testing for tertiary outcomes because they are considered exploratory in nature.

The total hospitalizations and total days of hospitalization will be analyzed using generalized Poisson or negative binomial regression models. If extra zero counts are observed in the above, a zero inflated Poisson model will be used³⁴. In the generalized mixed model, covariates will include site as a random effect, and general health status (Charlson <3 versus ≥ 3 , or as continuous variable) as a fixed effect. Proportion of participants requiring at least one hospitalization will be analyzed using a chi-square test statistic.

Considering informative censoring due to death if there is a treatment effect, we will also summarize hospitalization rate and days of hospitalization based on total active follow-up time. Similar tests as described above will be processed.

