While these lifestyle modifications cannot be mandated, participant compliance with these conventions will be strongly encouraged. Per clinical trial evidence linking outcome to dose, all participants will be strongly recommended to be on maximum tolerated doses of a beta blocker and an ACE inhibitor or ARB⁷⁴ to be eligible for entry into the study. Optimal medical therapy was chosen to explicitly test the efficacy and safety of the ICD on top of guideline-driven medical care.

D. Outcome Measures and Rationale

This study is designed to compare the efficacy and safety of ICD implantation in an aged population in reducing all-cause mortality. The primary outcome is measured by survival time. The study is designed to detect 25% reduction in the hazard of all-cause mortality among participants randomized to ICD with an estimated average follow-up of 3.6 years. Key secondary analyses will be quality of life and the effect of ICD in high- versus low co-morbidity burden. Quality of life (QoL) will be measured by the Minnesota Living with Heart Failure

questionnaire, a cardiac disease-specific QoL instrument. Quality of Life will be measured at baseline, six months, twelve months, and twenty-four months.

E. Sample Size

The target sample size for CSP #592 is 1,462 total participants (731 per treatment group to achieve a total of 565 primary outcome events). This sample size will provide 90% power to detect a 25% reduction in hazard from all-cause mortality between ICD + OMT and OMT alone, and will provide ample power to identify clinically meaningful differences between treatments in longer-term safety and Quality of Life measures, as well as significance in the treatment interaction based on co-morbidity burden.

F. Data Collection and Assessments

Study participants will be assessed at baseline via in-person clinic visit and at month 1 to 4 following randomization and every 6 months thereafter via phone-based centralized follow-up; information related to the device will be collected on the day of implantation. The maximum follow-up is 5 years, the average participant follow-up across all participants (recruited in the pilot and full-scale stages) is 3.6 years. Chapter VIII provides details of the baseline assessments and procedures and Chapter 0 describes details of the follow-up schedule and procedures.

G. Alternate Design Considerations

1. Age Eligibility Criterion

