1.3.2.4 All-Cause Hospitalization

Hospitalization information will be captured by participant self-report and medical record review. Self-report is valid and reliable, especially with inpatient care and recall periods less than one year²³; however, hospitalization data will also be collected from VA electronic medical records, and where feasible: access of non-VA medical records.

Specifically, this study will test whether the total number of days of hospitalization are different between the two treatment arms.

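### The zero-inflated Poisson fallback in SAP 2.2.7.2 drops the overdispersion term, so once it is used, standard errors for total hospital days are much too small

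*Combined protocol and SAP*

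**What the plan says.** For both counts, SAP 2.2.7.2 starts from this rule: "The total hospitalizations and total days of hospitalization will be analyzed using generalized Poisson or negative binomial regression models." Either model carries a dispersion parameter. The arms are "compared between treatment groups at a 0.05 significance level". The fallback follows at once: "If extra zero counts are observed in the above, a zero inflated Poisson model will be used." In the mixed model, "covariates will include site as a random effect, and general health status" (Charlson score) as a fixed effect.

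The section has no participant-level random effect, no robust or scaled standard error, no zero-inflated or hurdle negative binomial, and no check for overdispersion left among the non-zero totals. It does not say what makes zeros *extra*, or against which model that is judged. The additional analysis based on active follow-up time reuses similar tests.

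Protocol XV.C.4.b says the same two counts "will be analyzed using generalized Poisson or negative binomial regression models" and has no fallback, so the zero-inflated Poisson step is an SAP addition.

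SAP 1.3.2.4 says the study will test whether "the total number of days of hospitalization are different between the two treatment arms". On status, SAP 2.2.7.2 states: "No adjustment will be made for multiple testing for tertiary outcomes because they are considered exploratory in nature." Protocol II.D and SAP 1.2.4.2 also place hospitalization under exploratory analyses. However, the overview in Protocol III.A counts it among the secondary objectives, and SAP 1.3.2.4 sits under the secondary outcome measures.

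**The concern.** A zero-inflated Poisson explains excess variance only through its class of structural zeros. Among everyone else it assumes variance equal to the mean. Total days break this by construction: a stay is several days at a time, and a few participants accumulate very long totals. Admissions also vary between participants beyond Poisson variation. A site random effect cannot absorb differences between participants at the same site.

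The rule therefore moves from models that can represent this variation to one that cannot. The direction of the error is known in advance: standard errors too small, intervals too narrow, p-values too low. SAP 2.2.3 promises p-values for exploratory endpoints as well, and Protocol XVIII.B plans a paper on secondary and exploratory outcomes. A false difference in hospital days, in either direction, would colour how the benefit and burden of an implanted device are read.

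**Working it through.** The documents give no admission rate, length of stay, dispersion or fraction with no admission, so there is no planned figure to reproduce. The size has to come from simulation over stated assumptions.

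**Inputs from the documents.** Protocol III.E: "The target sample size for CSP #592 is 1,462 total participants", 731 per arm. SAP 2.1: full-scale follow-up of 2 to 5 years and 15% annual control-arm mortality. SAP 2.2.7.2: 0.05 level, taken as two-sided.

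**Assumed inputs.** 0.3–1.2 admissions per year; between-patient gamma variance k of 0–2; structural zeros 0–30%; mean stay 3–5 days.

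**Method.** Both arms were generated identically. Each data set was fitted by maximum likelihood with a negative binomial and with a zero-inflated Poisson (inflation either common or arm-specific). The Wald test rejected at |z| > 1.96. There were 1,000 trials per setting, or 300 for the common-inflation fit, so the Monte Carlo standard error at a 50% rejection rate is √(0.25/1000) = 1.6 points, or √(0.25/300) = 2.9 points. Site, Charlson score and a follow-up offset were left out.

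**Zero-inflated Poisson under the null, nominal 5%:**

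| Outcome | k | Rejection | Model SE too small by |
|---|---|---|---|
| Admissions | 0 | 6–7% | 3–6% |
| Admissions | 0.5 | 10–12% | 15–22% |
| Admissions | 1 | 20–36% | 34–55% |
| Admissions | 2 | 32–39% | 48–56% |
| Days | 0 | 25–48% | 39–62% |
| Days | 0.5–1 | 37–65% | 54–77% |

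On the same data, the negative binomial rejected in 3.7–6.2% of trials for admissions and 1.2–2.2% for days. It removes the inflation but is conservative for days.

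**Closed-form check for days.** Let r = Var(Y | Y>0) / E(Y | Y>0). When the non-zero mean is well above zero, the ratio of model SE to true SE is about 1/√r, and null rejection is about 2{1 − Φ(1.96/√r)}.

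- Lightest days setting (0.3 per year, k = 0, 30% structural zeros, mean stay 3). Simulated data: mean 1.66, zeros 0.64, variance/mean 5.6.
  - Non-zero mean: 1.66/0.36 = 4.61.
  - E(Y²): 5.6×1.66 + 1.66² = 12.05; among non-zeros, 12.05/0.36 = 33.5.
  - Non-zero variance: 33.5 − 4.61² = 12.2, so r = 12.2/4.61 = 2.65.
  - SE ratio 0.61 and rejection about 23%. Simulated: 0.59–0.61 and 25–26%.
- Heaviest days setting (0.8 per year, k = 1, 20% structural zeros, mean stay 5). Simulated data: mean 8.44, zeros 0.50, variance/mean 26.7.
  - Non-zero mean: 8.44/0.50 = 16.88.
  - E(Y²): 26.7×8.44 + 8.44² = 296.6; among non-zeros, 593.1.
  - Non-zero variance: 593.1 − 16.88² = 308.2, so r = 18.3.
  - SE ratio 0.23 and rejection about 65%. Simulated: 0.23–0.24 and 65%.

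**Would the fallback be triggered?** Because the SAP gives no criterion, one check counted zeros as extra when they exceeded the negative binomial prediction by more than 1.96 binomial standard errors (mean stay 4.5 days, k of 0.5–2, structural zeros 0–20%, 27 settings of 40 trials). For admissions it never fired. For days it fired in 0–3% of trials at 0.3 admissions per year, 0–100% at 0.6, and mostly 88–100% at 1.2. A further simulation agreed for admissions and at the lowest rate, and gave 47–100% for days at the higher rates. In that simulation, judging zeros against a Poisson fit fired the trigger every time.

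**The case against.** The strongest reply has four parts.

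1. *Status.* Hospitalization is exploratory in its own sections, and Protocol XV.A.3 and SAP 2.1 give everything beyond the primary endpoint only an exploratory interpretation. No sample size, stopping rule or mortality test uses this model. This stands, and it limits the severity. It does not excuse the standard errors: exploratory status justifies leaving out multiplicity adjustment, not using a variance assumption known to fail.

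2. *The rule is conditional.* A reader might infer that following the SAP gives a false difference in hospital days about half the time, or that frequent zeros alone bring in the fallback. The documents do not support either. The first-line models carry dispersion, and the switch needs extra zeros, most naturally read as zeros beyond what those models fit. The 25–65% applies once the fallback is in use. How often that happens depends on unknown rates and an unstated criterion.

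3. *Admissions.* A reader might infer the same damage for both counts. That is not supported: inflation for admissions is slight when structural zeros and follow-up explain the excess variance, and the trigger did not fire against a negative binomial fit.

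4. *Model and safeguards.* The simulations left out site and Charlson score, so the exact percentages are not those of the SAP model, although neither term removes variation between participants within a site and Charlson stratum. The chi-square test of any hospitalization is unaffected by the fallback. The analysis by active follow-up time gives no protection, because it reuses similar tests.

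**Conclusion.** The point holds, mainly for total hospital days, and the sentence is wrong as written. Once the zero-inflated Poisson is used, model standard errors for days are 39–77% too small and null rejection is roughly 25–65% at nominal 5%. The failure persists with no between-patient gamma variation at all (25–48%). For admissions the range is about 6–39%, material only with moderate to strong between-patient variation, and the fallback would rarely apply if judged against a negative binomial fit. If zeros are instead judged against a Poisson, overdispersion alone can trigger the switch, bringing in the replacement where it fits badly.

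All sizes depend on the assumed rates, stays and dispersion; the direction and mechanism do not. A reader might infer a threat to the trial's main result. There is none, because the mortality analysis does not use this model. The point is a should-fix.

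**What to change.** Delete the zero-inflated Poisson sentence from SAP 2.2.7.2. In its place, state that negative binomial regression is the analysis for both total admissions and total days. If observed zeros exceed those predicted by the fitted negative binomial by a criterion fixed in advance (the 1.96 binomial standard errors used above is one option), use a zero-inflated or hurdle negative binomial. Add robust standard errors for total days, where the plain negative binomial was conservative in the simulations. A permutation p-value is optional.

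The cost is one SAP sentence and a decision on the criterion before outcome data are seen. It needs no new data and no change to sample size or trial conduct, and it stays within the model family that Protocol XV.C.4.b already names.
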